## 1.2 OBJECTIVES

### 1.2.1 Primary objectives

The primary objective is to evaluate long-term safety of alemtuzumab.

### 1.2.2 Secondary objectives

The secondary objectives are:

- To evaluate long term efficacy of alemtuzumab.
- To evaluate the safety profile of patients who received other disease modifying therapy (DMT) following alemtuzumab treatment.
- To evaluate patient-reported quality of life (QoL) outcomes and health resource utilization of patients who received alemtuzumab.

- To evaluate as needed re-treatment with alemtuzumab and other DMTs.

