- During infusion: continuous or hourly monitoring BP/HR; intermittently ambulation, compressive stocking.
- Post infusion: inform/remind patient any abnormal clinical sign/symptoms related to infusion.
- Periodic liver function test.

Please refer to [Section 10.1.6](#) for details.

Study CAMMS03409 is an open-label extension study designed to provide additional safety monitoring for up to 60 months, and as-needed alemtuzumab retreatment to qualifying patients who received alemtuzumab in prior Genzyme-sponsored studies CAMMS223, CAMMS323 and CAMMS324. In addition, patients who received SC IFNB-1a in the earlier studies had the opportunity to receive 2 annual courses of alemtuzumab, and possibly subsequent as-needed alemtuzumab retreatment.

In CAMMS03409, “as needed” retreatment with alemtuzumab could be offered to patients upon documented evidence of resumed MS disease activity, subject to safety-related disqualifications. The additional course(s) of alemtuzumab were administered at 12 mg/day on 3 consecutive days (36 mg total dose) at least 12 months after the prior treatment course. The benefits and risks of >2 treatment courses have not been fully established, but results suggest that the safety profile does not appear to change with additional courses.

The present study LPS13649 will provide long term safety and efficacy data on the patients who completed the extension study CAMMS03409, as well as on additional as-needed alemtuzumab retreatment. In addition, the study will provide information about the safety profile of patients who received other commercial DMTs following alemtuzumab treatment.

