### **5.2 SECONDARY**

The secondary objectives are:

- To evaluate long term efficacy of alemtuzumab.
- To evaluate the safety profile of patients who received other DMT following alemtuzumab treatment.
- To evaluate patient-reported quality of life (QoL) outcomes and health resource utilization of patients who received alemtuzumab.
- To evaluate as needed re-treatment with alemtuzumab and other DMTs.

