## 6 STUDY DESIGN

### 6.1 DESCRIPTION OF THE PROTOCOL

This study is a Phase 3B/4, international, multicenter, open-label, non-comparative study to evaluate the long-term safety, efficacy and QoL of alemtuzumab in patients who have completed at least 48 months of the extension study CAMMS03409. In addition, impact of treatment on pharmaco-economic data will be evaluated.

Patients treated with alemtuzumab within 48 months prior to enrollment in the LPS13649 study must be followed-up at monthly intervals until 48 months after the last infusion of alemtuzumab ([Section 10.1.6.2](#)).

Scheduled visits for safety and efficacy assessments will be performed every six months. AEs and concomitant medications will be monitored continuously. Quality of life, pharmaco-economic data and brain imaging will be collected every twelve months.

Patients must contact the treating neurologist at the study site (Study Investigator) as soon as they experience any sign or symptom of MS relapse. The Study Investigator will decide on the need to schedule extra visits (unscheduled visits) to evaluate the patient's status. All procedures and assessments will be collected in the e-CRF.

At the Study Investigator discretion patients can be treated:

- Patients may receive additional courses of alemtuzumab but not sooner than 12 months from any previous alemtuzumab treatment course, or
- Patients may receive other commercial DMTs.

In the event that a Study Investigator decides to treat a patient (with alemtuzumab or another DMT) the factors contributing to the decision to treat (eg, patient is experiencing clinical and/or imaging activity) should be documented in the e-CRF.

For treatment courses of alemtuzumab the Study Investigator should refer to the safety information in the Investigator's Brochure (IB) or in the approved label in the country/region when available. All treatment courses will consist of 12 mg/day alemtuzumab intravenously infused once daily on 3 days ([Section 8.1](#)).

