## **2.3 ANALYSIS POPULATIONS**

### **2.3.1 Safety populations**

All patients who have signed the ICF will be included in the safety population.

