#### **2.3.1.1 Retreated population**

The population is defined as safety patients who have received study drug in TOPAZ study.

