### **2.4.2 Prior or concomitant medications**

The concomitant medications will be presented for the enrolled population. All the medication that taken in TOPAZ study will be considered as concomitant medications.

Medications will be summarized in overall group and by subgroups (IAT vs DAT) according to the WHO-DD dictionary, considering the first digit of the anatomic category (ATC) class (anatomic category) and the first 3 digits of the ATC class (therapeutic category). All ATC codes corresponding to a medication will be summarized, and patients will be counted once in each ATC category (anatomic or therapeutic) linked to the medication. Therefore patients may be counted several time for the same medication.

The tables for concomitant medications will be sorted by decreasing frequency of ATC followed by all other therapeutic classes based on the incidence in the overall group. In case of equal frequency regarding ATCs (anatomic or therapeutic categories and/or generic names), alphabetical order will be used.

In addition, the alternative MS therapies will be summarized separately. Alternative MS medication will be determined based on the anatomic or therapeutic categories and generic name.

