#### **2.4.5 Analyses of safety data**

The summary of safety results will be presented in overall group and by subgroups (IAT vs DAT).

Only data collected in TOPAZ study will be used for analysis in addition of baseline information from previous studies.

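### The SAP plans no safety output for patients who took another DMT after alemtuzumab, although this is a stated secondary objective

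*SAP*

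**What the plan says.** The commitment is made three times. Protocol 5.2 lists as a secondary objective "To evaluate the safety profile of patients who received other DMT following alemtuzumab treatment". SAP 1.2.2 repeats it almost word for word: "To evaluate the safety profile of patients who received other disease modifying therapy (DMT) following alemtuzumab treatment". Protocol section 4 adds that "the study will provide information about the safety profile of patients who received other commercial DMTs following alemtuzumab treatment". Switching is part of the design: under Protocol 6.1, at the investigator's discretion, "Patients may receive other commercial DMTs". SAP 1.5 and 1.6 record no change to the protocol's statistical section, so the objective has not been withdrawn.

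On the analysis side, SAP 2.3.1 sets the main safety population: "All patients who have signed the ICF will be included in the safety population". For the retreated subset, SAP 2.3.1.1 says "The population is defined as safety patients who have received study drug in TOPAZ study", where study drug means alemtuzumab. SAP 2.4.5 fixes the grouping: "The summary of safety results will be presented in overall group and by subgroups (IAT vs DAT"). Other DMTs enter the planned outputs once, in SAP 2.4.2: "In addition, the alternative MS therapies will be summarized separately".

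**The concern.** A stated objective should lead to at least one output that reports on it. Here the population of interest is never formed, and the time of interest (after another DMT is started) is never separated. A reader of the study report would see how many patients took other MS therapies and, elsewhere, how many patients had each event, with nothing linking the two.

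Two things are at stake. The main one is that a secondary objective would go unreported. The lesser one is interpretation of the primary safety results. Infections, malignancy, PML and cytopenias that arise after a later immunotherapy enter the overall tables undistinguished. Protocol 8.8 itself warns of possible additive immune effects between alemtuzumab and other therapies.

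**Working it through.** The plan gives no figure to reproduce. There is no sample size calculation, no expected number of switchers and no expected event rate. The check is an inventory of the places where DMT status could have entered, followed by what can be said about size.

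**Inventory**

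- Populations (SAP 2.3): safety, retreated, 48-month follow-up, efficacy, IAT and DAT. None depends on another DMT taken after alemtuzumab.
- Event classification (SAP 2.4.5.1): every reported AE is treatment-emergent. There is no cut-off or period split at the start of another DMT.
- Percentages (SAP 2.4.5.1): the denominator is the whole safety population, overall and by IAT/DAT.
- Rates (SAP 2.4.5.1): SAEs and non-temporary AESIs are divided by total treatment exposure. Person-years (SAP 2.4.3.1) run to the end of TOPAZ and do not stop at a switch.
- AESIs over time (SAP 2.4.5.1): the intervals are numbers of alemtuzumab courses, or infusion days and the three days after.
- Deaths (SAP 2.4.5.2): on-study and post-study, with no DMT split.
- Listings (SAP 2.4.5.1): the columns include neither DMT status nor DMT start date.
- Relationship: Protocol 10.4.2 asks about the IMP or study procedures, not the other DMT. SAP 2.5.2 counts a missing assessment as related to the IMP.
- Protocol 11.4.2: adds no DMT analysis and defers to the SAP.

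The medication summary in SAP 2.4.2 contains no safety events. It bears on a different secondary objective, the one on as-needed re-treatment with alemtuzumab and other DMTs.

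**What can be said about size**

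Let x be the share of person-time after a switch and r the ratio of the event rate after the switch to the rate before it. Then

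pooled rate / pre-switch rate = 1 + x(r − 1).

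The documents give neither x nor r. With assumed values that allow r on both sides of 1:

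| r (assumed) | x = 2% | x = 30% |
|---|---|---|
| 0.5 | 1 + 0.02 × (−0.5) = 0.99 | 1 + 0.30 × (−0.5) = 0.85 |
| 1 | 1.00 | 1.00 |
| 1.5 | 1.01 | 1.15 |
| 2 | 1.02 | 1.30 |
| 3 | 1.04 | 1.60 |

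The pooled rate could be lower than, equal to or higher than the pre-switch rate.

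The inverse shows why the pooled tables cannot answer the objective. Suppose the pooled rate were 10% above the pre-switch rate. Then r = 1 + 0.10/x:

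- x = 2%: r = 6.0
- x = 5%: r = 3.0
- x = 10%: r = 2.0
- x = 20%: r = 1.5
- x = 30%: r = 1.33

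One pooled result fits very different post-switch profiles, and the pre-switch rate that would be needed is not tabulated either. The formula concerns event rates per unit of person-time. It does not carry over directly to the main AE tables, which count each patient once per event.

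**The case against.** The best defence is that counting every event during follow-up, whatever therapy came later, is a legitimate description for an open-label, non-comparative study without formal tests. Tables of events related to the IMP are also planned for TEAEs and SAEs. Both points are fair, and the pooled tables are not an error. The related-event tables, however, filter on investigator judgement about alemtuzumab and do not identify exposure to another DMT. Neither point supplies an output for the objective.

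A reader might also infer three stronger claims that the documents do not support.

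- *Every safety table mixes time before and after a switch.* Infusion-reaction tables cover the infusion and the next 24 hours. Tables of temporally associated AESIs cover the infusion days and three days after, in retreated patients. Infusion vital signs are analysed separately. Laboratory tables are confined to the retreated and 48-month follow-up populations. None of these answers the objective, but they are not study-long pooled tables.
- *The objective cannot be answered at all.* Protocol 8.8 and SAP 2.1.2 collect medications from the end of CAMMS03409 to the last visit. Protocol 6.1 requires the reasons for starting a DMT in the e-CRF. The listings carry patient identifiers and onset dates. The gap lies in the planned outputs, not in the data.
- *The alemtuzumab rates are inflated by a given percentage.* That requires assuming r above 1. Protocol 8.8 offers only a qualitative caution and no rate.

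**Conclusion.** The concern holds as a gap in planned outputs. Followed exactly, the SAP gives no safety result for patients who received another DMT after alemtuzumab, although both documents state this as a secondary objective. That conclusion comes from reading the populations, groupings and tables, and rests on no numerical assumption.

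The effect on the pooled AE, SAE and AESI results is of unknown size and direction. It is zero if r = 1, and the values in the table above are illustrations under assumption only, so no inflation figure should be claimed. The point matters enough that the SAP should be changed, but the objective is secondary and descriptive, and the gap can be closed before database lock.

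**What to change.** In SAP 2.3.1:

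- Define a population of patients who started another DMT after their first alemtuzumab dose. This excludes the SC IFNB-1a that DAT patients received beforehand.
- Identify patients already on such a DMT, or previously exposed to one, at D1. TOPAZ collects medications only from the end of CAMMS03409, so use CAMMS03409 medication data where available and say where they are not.
- State a rule for partial DMT start dates. SAP 2.5.2 does not impute medication dates, and a person-time split needs one.

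In SAP 2.4.5:

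- Add descriptive tables of AEs, SAEs, AESIs and deaths, giving patients and events per 100 patient-years, for time before or without another DMT and for time after its start.
- Show time after any later alemtuzumab re-treatment as a separate category. Protocol 8.8 foresees re-treatment of patients who are on another DMT. A single split at first DMT would put the resulting infusion reactions and AESIs under the other DMT.
- Use TOPAZ person-time as the denominator, because SAP 2.4.5 takes safety events from TOPAZ only.
- Add DMT status to the listings.

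Keep the pooled tables, and label the split descriptive and non-randomised. The cost is some derivations and a few extra tables, with small numbers in some cells.

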### 1.3 DETERMINATION OF SAMPLE SIZE

There are no sample size calculations for this long-term safety study. Sample size will be based on elective participation of patients who were enrolled (and completed at least 48 months) into the CAMMS03409 extension study.

[figure not shown]
### 1.4 STUDY PLAN

The whole clinical trial of alemtuzumab consists of three study periods:

CAMMS223/323/324 prior studies (2 years): to compare the efficacy and safety of alemtuzumab to subcutaneous (SC) interferon beta-1a (IFNB-1a, Rebif) in treatment-naïve patients with relapsing-remitting multiple sclerosis (RRMS) who had recent MS disease activity as demonstrated by clinical relapses.

CAMMS03409 extension study (at least 4 years): to examine the long-term efficacy and safety of alemtuzumab in MS patients who received alemtuzumab during prior studies CAMMS223/323/324 and the efficacy and safety of 2 fixed annual alemtuzumab courses in patients who previously received SC IFNB-1a during prior studies.

LPS13649 (TOPAZ) extension study (5 years): to evaluate the long-term safety, efficacy and Quality of life (QoL) of alemtuzumab in patients who have completed at least 48 months of the extension study CAMMS03409.

- ★ Only for patients treated with alemtuzumab: monthly laboratory safety variables collection for 48 months after last infusion
  - For patients who received alemtuzumab in CAMMS03409 study less than 48 months before entering in LPS13649 study, and
  - For patients receiving retreatment with alemtuzumab during the LPS13649 study
- \* After completion of 5 years of the first patient inclusion, the next scheduled visit for any patient will be performed as EOS visit.

Scheduled visits for safety and efficacy assessments will be performed every six months. AEs and concomitant medications will be monitored continuously. Quality of life, pharmaco-economic data and brain imaging will be collected every twelve months (Table 1).

**Table 1 – Study flow chart**

	Selection visit (D1)	Study assessments each year		Unscheduled visits	EOS
		Scheduled visits			
		6 M	12 M		
Informed consent signature	X				
Inclusion Exclusion criteria verification	X				
AE reporting	X	X	X	X	X
Vital signs	X a	X	X	X	X
Physical examination including weight b	X a		X		X
MS relapse verification	X	X	X	X	X
EDSS	X a	X	X	X	X
Brain Imaging	X c		X		X c
SF-36 - FAMS - EQ-5D	X a		X		X
Modified HRUQ/HRPQ	X d		X		X
Record concomitant medication	X	X	X	X	X
Collection of blood samples for PGx assessment e		X f	X f	X f	X f

a If not performed in the previous 3 months.

b Note that weight assessment is included in the vital signs assessment module in the eCRF instead of the physical examinations module. Nevertheless, it is to be performed at baseline and on yearly basis and not every 6 months.

c If not performed in the previous 6 months.

d If the HRUQ questionnaire was administered in the previous 3 months, then only questions 1 through 9 of the Modified HRUQ/HRPQ need to be completed at baseline.

e For consenting patients only.

f Omit if collected at a previous visit.

For all the patient retreated with alemtuzumab and for 48 months after last infusion (Table 2).

**Table 2 - Re-treatment with Alemtuzumab Flow Chart**

	Prior to treatment	During 48 months											
		1 M	2 M	3 M	4 M	5 M	6 M	7 M	8 M	9 M	10 M	11 M	12 M
Pregnancy test (in women of childbearing potential)	X												
ECG	X												
HPV (only in women)	X a												X
CBC with differential (including platelet count)	X b	X	X	X	X	X	X	X	X	X	X	X	X
Serum Creatinine and LFT (liver function tests)	X b	X	X	X	X	X	X	X	X	X	X	X	X
Urinalysis with microscopy	X b	X	X	X	X	X	X	X	X	X	X	X	X
TSH	X b			X			X			X			X
Study Investigator review of labs	X	X	X	X	X	X	X	X	X	X	X	X	X

Monthly safety laboratory assessment will be performed in local laboratories at the patients' convenience.

- a If not performed in the previous 12 months. In addition, an HPV screening should be performed approximately 1 year after the last alemtuzumab infusion date, and then every 12 months until the 48 months safety follow-up is completed. For women patients re-treated with alemtuzumab during the study, an HPV screening should be performed prior to re-treatment (if not performed in the previous 12 months) and then every 12 months until the 48 months safety follow-up is completed.
- b If not performed in the previous 2 weeks. LFT includes: ALT, AST, ALP, albumin, total protein, total bilirubin, and direct bilirubin.

## 1.5 MODIFICATIONS TO THE STATISTICAL SECTION OF THE PROTOCOL

Not applicable.

## 1.6 STATISTICAL MODIFICATIONS MADE IN THE STATISTICAL ANALYSIS PLAN

Not applicable

## 2 STATISTICAL AND ANALYTICAL PROCEDURES

### 2.1 ANALYSIS ENDPOINTS

#### 2.1.1 Demographic and baseline characteristics

The TOPAZ baseline value is defined as the available value assessed on or prior to the V01 Selection visit, unless otherwise specified. The last available value in previous studies can be considered as the baseline if they were evaluated within the pre-specified time window. For brain imaging result, if the last non-missing assessment performed within 6 months prior to the V01 selection visit, it can be considered as baseline. For vital sign, physical examination, EDSS and questionnaires, the time window is 3 months.

For efficacy endpoints (EDSS, MRI), the baseline from prior studies will be considered as long-term baseline, which is defined as last available assessment prior to first dose of alemtuzumab or SC IFNB-1a administration.

All baseline safety and efficacy parameters (apart from those listed below) are presented along with the on-treatment summary statistics in the safety and efficacy sections ([Section 2.4.5](#) and [Section 2.4.4](#)).

#### *Demographic characteristics*

Demographic variables are:

- Age (quantitative and qualitative variable: <65, [65 – 75] and >75 years)
- Sex (Male, Female)
- Race (White, Black, Asian, American Indian or Alaska Native, Native Hawaiian or Other, Pacific Islander, Other)
- Ethnicity (Hispanic/Latino, Not Hispanic/Latino)
- Weight
- Height
- Body Mass Index (BMI)
- Geographic Region (USA/Canada/Australia, Latin America, EU, Non-EU Europe and Israel)
- Time since first dose of alemtuzumab infusion (in years)

#### *Baseline Physical Examination*

Baseline physical examination, i.e., number (%) of patients who are normal/abnormal at baseline will be summarized.

### ***Disease characteristics at baseline***

Specific disease history includes

- Baseline EDSS (TOPAZ baseline and long-term baseline)
- Time (years) since initial/last clinical episode
- Brain imaging characteristics (e.g. Gadolinium-Enhancing lesion count, T1-Hyperintense Lesion Volumes and T2-Hyperintense Lesion Volumes) (TOPAZ baseline and long-term baseline)

Any technical details related to computation, dates, and imputation for missing dates are described in [Section 2.5](#).

#### **2.1.2 Concomitant medications**

A concomitant medication is any treatment received by the patient concomitantly to any investigational medicinal product (IMP)(s) in the current study, all medications received by the patient from the end of the Extension Study CAMMS03409 to Visit 1 of LPS13649 study, and during the TOPAZ study until the last visit will be collected.

Any technical details related to computation, dates, imputation for missing dates are described in [Section 2.5](#).

#### **2.1.3 Efficacy endpoints**

Efficacy endpoints are considered as secondary objective.

The long-term effects of alemtuzumab will be examined by summarizing from baseline through the last study visit of our study by the following efficacy endpoints:

- Annualized relapse rate (ARR)
- Proportion of patients relapse free
- Change over time in Expanded Disability Status Scale (EDSS) scores
- Change over time in brain imaging characteristics to include:
  - Number of Gadolinium (Gd)-enhancing, and new Gd-enhancing lesions
  - Number of new/enlarging T2 lesions
  - Number of new T1 (and new hypointense T1) lesions
  - T1 and T2 lesion volume
  - Brain Parenchymal Fraction (BPF)

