#### **2.1.3.1.2 Proportion of Patients who are Relapse Free**

Patients will be considered relapse free at each measurement time and at the end of the study if they did not experience a protocol defined relapse in the relevant time period.

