### **2.3.2 Efficacy populations**

The population on which efficacy analyses will be performed consists of all enrolled patients who have received study drug in CAMMS223, CAMMS323, CAMMS324 or CAMMS03409.

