##### **2.4.4.1 Analysis of efficacy endpoint(s)**

###### **2.4.4.1.1 Annualized relapse rate (ARR)**

The estimated annualized relapse rate using negative binomial model with robust variance estimation will be presented by year and in overall. The observed total number of relapses is the dependent variable, the log total amount of follow-up time in years for each patient will be the offset variable and analysis group indicator (IAT vs DAT) and geographic region will be the covariates in the model. Both IAT vs DAT comparison and ARR by alemtuzumab courses will be analyzed. The analysis period starts from prior studies (CAMMS323/324) until the end of TOPAZ study. The model will also be stratified by previous clinical study.

The observed annualized relapse rate will be reported as well, which is defined as the total number of relapses divided by the total years of follow-up for each patient.

The ARR will be presented separately for retreated population in overall group.

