#### *2.4.4.1.3 EDSS*

The observed value, change from baseline as well as percentage change from baseline will be presented descriptively. The change from baseline in EDSS will be analyzed using a mixed model for repeated measures (MMRM) (7)(8)(9) with baseline EDSS score, analysis group indicator (IAT and DAT), geographic region, study visit and study visit by analysis group interaction as covariates. The TOPAZ study baseline at study entry is considered as post-baseline for efficacy analysis. The comparison of the change from baseline in EDSS with the MMRM will include the change from baseline to each consecutive year which can be constructed using the linear contrasts of the estimated regression parameters. All post-baseline EDSS scores will be included in the MMRM; patients without any post-baseline scores will not be included. For this model, imputation will not be used.

Similar analysis for change of EDSS by alemtuzumab courses and for retreated population will be analyzed as well.

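### Relapse, EDSS and MRI results over all follow-up are presented as effects of alemtuzumab, although patients may start another DMT and stay in the analysis

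*SAP*

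**What the plan says.** Protocol 6.1 leaves further treatment to the investigator. Besides more alemtuzumab, "Patients may receive other commercial DMTs". Clinical or imaging activity is named there as an example of the reason, and the reason is to be recorded. Protocol 10.1.5 repeats the permission. Starting another DMT does not end follow-up.

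The efficacy plan runs as follows.

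- **Target (SAP 2.1.3, likewise Protocol 9.2):** "The long-term effects of alemtuzumab will be examined by summarizing from baseline through the last study visit of our study".
- **Population (SAP 2.3.2):** "The population on which efficacy analyses will be performed consists of all enrolled patients who have received study drug" in an earlier study. There is no condition on later DMT use.
- **ARR (SAP 2.4.4.1.1):** "The analysis period starts from prior studies (CAMMS323/324) until the end of TOPAZ study", and "the log total amount of follow-up time in years for each patient will be the offset variable".
- **Relapse free (SAP 2.1.3.1.2):** patients qualify "if they did not experience a protocol defined relapse in the relevant time period". The Kaplan-Meier and Cox analyses in SAP 2.4.4.1.2 have no rule at DMT start and no DMT covariate.
- **EDSS (SAP 2.4.4.1.3):** "All post-baseline EDSS scores will be included in the MMRM; patients without any post-baseline scores will not be included". SAP 2.1.3.2 and 2.4.4 narrow this: unscheduled scores are left out of the change analysis (early discontinuation excepted), and only TOPAZ data plus the earlier baseline are used.
- **MRI (SAP 2.4.4.1.4 and 2.4.4.1.5):** the models adjust for baseline, group and region only.

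Results are split by IAT/DAT, by number of alemtuzumab courses and for the retreated population, but not by other DMT. The one analysis of other DMTs is in SAP 2.4.2: "In addition, the alternative MS therapies will be summarized separately". That medication table is tied to no endpoint. The missing-data rules in SAP 2.5.2 do not mention switching, and Protocol 11.4.1 defers the detail to the SAP.

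**The concern.** Take a patient moved to another DMT because of new lesions, who then has quiet years. Those years enter the ARR denominator, the later EDSS scores enter the mixed model, and the later scans enter the MRI summaries. All of it is presented under the heading of alemtuzumab's long-term effects. If switching follows disease activity, the second drug is added in patients selected for doing badly, and any control it brings is credited to the first drug.

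The endpoints are not equally exposed. Relapse-free status is time to first relapse, so a patient switched after a relapse is already an event. Only switches before any relapse matter, for example those made for imaging activity. ARR, EDSS and MRI keep accruing after the switch and are more exposed.

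SAP 2.4.4 makes IAT versus DAT the main long-term efficacy analysis, and unequal switching can create or hide a difference there. The split at three courses has a related weakness: a patient given another DMT instead of a further course stays in the lower-course group.

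**Working it through.** The plan states no relapse rate, DMT-use rate, power or event count, so there is no figure of its own to reproduce. The calculation below only shows how large the effect could be. Every rate in it is an assumption.

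**Inputs from the documents.** TOPAZ lasts 5 years. The full ARR period is 2 + 4 + 5 = 11 years, taking the minimum extension length (SAP 1.4). At most 1248 patients enter (Protocol, Clinical Trial Summary).

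**Assumed inputs.** Patients who never switch relapse at r0 = 0.15 per year. Switchers would relapse at rs = 0.30 or 0.50 without the second drug and at rd = 0.15 on it. The share switching, f, is 5% to 30% (62 to 374 of 1248). The switch comes at TOPAZ entry or 2.5 years later, that is at s = 0 or 2.5 of 5 years, or s = 6 or 8.5 of 11 years.

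**Step 1: ARR in a single group.**

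- Planned (all follow-up of length T): (1 − f)·r0 + f·[s·rs + (T − s)·rd]/T
- Had no second drug been given: (1 − f)·r0 + f·rs

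For f = 20%, rs = 0.50, s = 0, T = 5:

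- planned = 0.8 × 0.15 + 0.2 × 0.15 = 0.150
- no second drug = 0.8 × 0.15 + 0.2 × 0.50 = 0.220
- understatement = 0.070/0.220 = 31.8%

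| T (years) | f | rs | s (years) | Planned | No second drug | Understated by |
|---|---|---|---|---|---|---|
| 5 | 5% | 0.30 | 2.5 | 0.1538 | 0.1575 | 2.4% |
| 5 | 20% | 0.50 | 2.5 | 0.185 | 0.220 | 15.9% |
| 5 | 20% | 0.50 | 0 | 0.150 | 0.220 | 31.8% |
| 5 | 30% | 0.50 | 0 | 0.150 | 0.255 | 41.2% |
| 11 | 5% | 0.30 | 8.5 | 0.1558 | 0.1575 | 1.1% |
| 11 | 20% | 0.50 | 6 | 0.188 | 0.220 | 14.5% |
| 11 | 30% | 0.50 | 6 | 0.207 | 0.255 | 18.7% |

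The 11-year rows hold rates constant and assume no switch before TOPAZ.

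**Step 2: if activity would have fallen anyway.** Take a late year with all switches made, stayers at 0.10 and switchers at 0.15 on the second drug, 20% switched. The planned figure is 0.8 × 0.10 + 0.2 × 0.15 = 0.110.

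- Switchers at 0.40 without the drug: 0.160, so understated by 0.050/0.160 = 31%.
- Switchers at 0.20 without the drug: 0.120, so understated by 0.010/0.120 = 8%.

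The assumed untreated course drives the result.

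**Step 3: IAT versus DAT.** Give both groups the same mix, 70% at 0.15 and 30% at 0.50, with no true difference. Switch a share f of all patients, drawn from the high-rate part, to 0.15 from entry. The ARR is 0.7 × 0.15 + (0.3 − f) × 0.50 + f × 0.15.

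- f = 10% in IAT: 0.220; f = 20% in DAT: 0.185; ratio 1.19.
- f = 5% in IAT: 0.2375; f = 25% in DAT: 0.1675; ratio 1.42.

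Exchange the two shares and the ratio inverts. The direction is not fixed.

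**Step 4: does cutting at the switch solve it?** No.

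- Step 1, 20% switched at entry: the cut figure is 0.150, the same as planned, against 0.220.
- Step 1, 20% switched at 2.5 years: (0.8 × 5 × 0.15 + 0.2 × 2.5 × 0.50)/(0.8 × 5 + 0.2 × 2.5) = 0.85/4.5 = 0.189, against 0.185 planned and 0.220.
- Step 2, first case: 0.100, further from 0.160 than the planned 0.110.

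**The case against.** The strongest defence is that reporting all follow-up is a sound treatment-policy summary in an open-label, non-comparative study that openly allows other DMTs. Efficacy is a secondary objective, and Protocol 11.4 plans no formal hypothesis tests. This stands as far as it goes, and the analysis should be kept. It does not answer the labelling point: the SAP never names the strategy and calls the result an effect of alemtuzumab.

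Three stronger readings are tempting, and the documents do not support them.

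- A reader might infer that the results are known to be biased by a large amount. Switching and relapse rates are not given, Protocol 6.1 offers disease activity only as an example of the reason, and patients picked at a time of high activity may improve without the new drug.
- A reader might infer that the bias must grow each year because the share on another DMT can only rise. Protocol 8.8 says patients should stop other DMTs if they are to be re-treated with alemtuzumab, so patients can leave that group. Only the share who have ever started one accumulates, and only among those still followed.
- A reader might infer that data up to the switch give the effect of alemtuzumab alone. Step 4 shows they need not, because the patients removed may be those doing worst.

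Counting a DMT start as failure is also imperfect. Some starts may have other reasons; Protocol 10.1.6, for instance, lists contraindications to alemtuzumab re-treatment.

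**Conclusion.** The point holds as a matter of labelling and missing supplementary analysis. The planned figures describe alemtuzumab with or without a later DMT. They cannot support statements about alemtuzumab alone, and nothing else in the SAP's efficacy analyses does.

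Single-group figures are too favourable if other DMTs are started for disease activity and work. Under the assumed rates above, ARR is understated by about 2% to 41% over TOPAZ and 1% to 19% over 11 years, and by less if activity would have fallen anyway. The true size cannot be derived from the documents. For IAT versus DAT the direction depends on which group switches more.

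**What to change.** In SAP 2.4.4:

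1. Keep the all-follow-up analyses and label them *alemtuzumab with or without later DMT*.
2. Beside each yearly result, by IAT/DAT and by number of courses, show the number of patients and the share of person-time on or after another DMT, with the recorded reason.
3. Add a supplementary Kaplan-Meier and Cox analysis with the event defined as first relapse or first start of another DMT after the first alemtuzumab course, so that the DAT patients' initial SC IFNB-1a does not count. Repeat it counting only DMT starts recorded as due to clinical or imaging activity.
4. Show ARR before and after DMT start, and EDSS and MRI up to DMT start, as descriptive only. State that they are subject to informative censoring and are not the basis for statements about alemtuzumab alone.

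Run item 3 from TOPAZ entry. Medications are collected only from the end of CAMMS03409 onward (Protocol 8.8, SAP 2.1.2), so report patients already on another DMT at entry separately. Extend the analysis back to CAMMS323/324 only if DMT dates are obtained along with the prior-study relapse data that SAP 2.4.4 already calls for. Add a rule for partial DMT start dates, because SAP 2.5.2 bars imputing medication dates.

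The cost is SAP wording, re-runs of methods already planned and some extra data handling. The supplementary relapse-free figure will probably be less favourable.
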